## 4.0 Test Schedule

	Baseline/Prior to Registration	Randomized Treatment Period (Day 1-Day 14)			Follow-Up Evaluation	
		Day 0 ( $\leq 2$ days)	Day 1 (1 st Dose)	Day 2-13 (l)	Day 14	Day 28 (k)
Informed Consent (a)	X					
Complete medical and surgical history	X					
Update of medical history	X					
Record medications and therapies (b)	X					
Record Concomitant medications		X	X	X	X	X
Height (c)	X					
Body weight	X			X		
Comprehensive physical examination (d), (o)	X			X	X	X
Targeted physical examination (e), (o)	X		X	X		
Vital Signs (f), (o)	X	X	X	X	X	X
12-Lead ECG	X			X		
Chest CT					X	X
CBC with differential (g)	X			X	X	X
Comprehensive metabolic panel (g)	X			X	X	X
Procalcitonin, IL-6, ferritin, azotemia, Ca, triglycerides, glucose, LDH, GGT, CPK, D-dimer, PT/INR, fibrinogen, and troponin		X		X	X	X
Thrombotic Events (m)			X	X	X	X
Renal profile (g)	X		X	X	X	X
Urinalysis with microscopic (g)	X			X		
Serum pregnancy test for WCBP	X				X	X
Urine pregnancy test for WCBP	X					
Ordinal Scale Assessment (h)	X		X	X	X	X
PCR based COVID-19 test (i)	X		Only Day 7	X	X	X
SpO2 by pulse oximetry with FiO2 (j)	X	X	X	X	X	X
Blood sample for future analysis (See Section 9.0) R		X	Only Day 7	X	X	X
Blood Sample for GBPA (See Section 9.0) R		X	Only Day 7	X	X	X

Stool (See Section 9.0) n, R		X	Only Day 7	X	X	
Saliva (See Section 9.0) R		X	Only Day 7	X	X	
PBMC (See Section 9.0) R		X				X
Nasal Pharyngeal (See Section 9.0)		X	Only Day 7	X	X	X
Adverse Event Evaluation		X	X	X	X	X

- a. ICF must be signed prior to performing Baseline evaluations.
- b. Record medications and therapies taken or received within 30 days prior to Baseline (or longer for investigational drugs for which 5 half-lives of the drug exceed 30 days).
- c. If subject is able to stand.
- d. Comprehensive physical examination will include the following organ or body system assessments: skin; head, eyes, ears, nose, and throat; thyroid; lungs; cardiovascular; abdomen (liver, spleen); lymph nodes; and extremities, as well as an abbreviated neurological exam.

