#### 13.4 Planned Analyses

##### Primary Analysis

Frequency distributions and chi-square tests will be used to screen for major imbalances in the two randomization groups for qualitative variables; graphical displays including box plots and summary statistics (e.g., mean, median, standard deviation, ranges, etc.) will be used for quantitative variables with t-tests (after appropriate transformations if necessary to meet the assumptions of the methods).

The primary outcome will include the number of patients who are alive AND free from respiratory failure at Day 28 divided by the total number of patients in each arm. This endpoint will be analyzed in a binary fashion using properties of the binomial distribution and will be compared between randomized arms by the use of independent samples Z-test for proportions and a 95% confidence interval will be constructed for the difference between arms. Proportions will also be compared using Cochran-Mantel-Haenszel tests, including the stratification factors of age and baseline disease severity. Multivariable logistic regression models will be used to assess the influence of treatment while controlling for covariates of interest (gender, symptom onset, comorbidities) along with stratification factors. Primary analysis for this efficacy outcome will include all participants who are randomized and received at least 1 dose of study treatment. Participants will be analyzed according to the treatment to which they were randomized.

Efforts to minimize loss to-follow-up will be considerable. However, small amounts of missing data may occur. In such cases, participants without Day 28 outcome data will be excluded from the analysis. Sensitivity analyses will evaluate the impact of making different assumptions about the missing observations.

**Interim analyses:** Two interim analyses will be conducted after 25% and 50% of patients have completed the 28 day study period. The interim analysis will include the below stopping rules for efficacy and futility based on a Lan-DeMets spending function with O'Brien-Fleming boundaries. Occurrence of adverse events will also be evaluated at the interim analysis.

Accrual	Control arm (#)	Camostat arm (#)	Total number (#)	Efficacy boundary (Z scale)	Alpha spent	Futility boundary (Z scale)	Beta spent
25%	33	33	66	+/- 4.33	0.001	+/- 0.007	0.002
50%	66	66	132	+/- 2.96	0.003	+/- 0.34	0.04
100%	132	132	264	+/- 1.97	0.05	+/- 1.97	0.20

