#### 13.5 Secondary Analyses

1. Proportion of patients alive AND free of ventilator use / ECMO at Day 28: The proportion will be evaluated based on the number of patients who are alive AND free of

ventilator use or ECMO at Day 28 after study entry divided by the number of total patients enrolled for each treatment arm. The proportion of patients who have this event will be analyzed similarly to the primary endpoint. Comparisons will be done by use of independent samples Z-test for proportions and a 95% confidence interval will be constructed for the difference between groups. The Cochran-Mantel-Haenszel test will be used to include stratification factors. Multivariable logistic regression models will be used to assess the influence of treatment arm on while adjusting for other factors of interest.

**2. Time to death and Mortality rate:** The Kaplan-Meier method will be used evaluate differences in the distributions of time-to-death between treatment arms. Rates of mortality at day 28 and day 56 mortality will be estimated. Patients lost to follow-up or who withdraw early will be considered censored at their last assessment date for the Day 28 rate. The stratified log-rank test will be used to compare differences in distributions of time to death based on stratification factors. Cox proportional hazards model will be used to compare treatment arms with inclusion of stratification factors or adjustment for covariates of interest.

**3. Time to clinical improvement:** Time to clinical improvement will be evaluated using Kaplan-Meier methods and Cox regression models. Rates of clinical improvement at days 14 and 28 will be estimated. Time to clinical improvement will be assessed after all patients have reached day 14 and 28; no clinical improvement at day 14 or 28 or death before day 14 or 28 will be considered as right censored. Hazard ratios with 95% confidence intervals will be calculated by the Cox proportional-hazards model. Covariates of interest will be included in regression models.

**4. Clinical status at Days 14 and 28:** The distribution of the clinical status will be summarized by arm at days 14 and 28. A proportional odds model with treatment arm and disease severity at baseline as covariates will be used to evaluate whether the odds of improvement on the ordinal scale are higher for the treatment arm as compared to control.

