### 13.6 Sample Size

Randomization will be done according to a 1:1 ratio. Based on data from Wang et al, 82% of patients treated with Remdesivir were alive and free from respiratory failure at day 28. In the preliminary report of Remdesivir for the treatment of COVID-19 in 1059 hospitalized patients, approximately 70% of patients treated with Remdesivir were alive and free from respiratory failure at Day 15; Day 28 data are not yet available. Using an expected proportion of 80% for the SOC control arm, this study would require 132 patients in each arm (total of 264 patients). Sample sizes of 132 in each arm achieves 80% power to detect a difference between the group proportions of 12% for the primary endpoint. The proportion in the treatment arm is assumed to be 80% under the null hypothesis and 92% under the alternative hypothesis. The proportion in the SOC arm is 80%. The test statistic used is the two-sided Z-Test with unpooled variance. The significance level of the test is 0.05 (two-sided).

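### Baseline SpO2/FiO2 and age in years are available, but the adjusted analyses in 13.4 use only an age cut at 65 and a two-level severity stratum, so a modest gain in precision is not taken

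*Combined protocol and SAP*

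**What the plan says.** - **Oxygenation.** Section 4.0 schedules "SpO2 by pulse oximetry with FiO2" before registration and at each later column; footnote j asks for FiO2 at the same moment. No primary, secondary, subgroup or exploratory analysis in Section 13 names it.
- **Age.** Section 5.1 and the subgroup list in 13.5 use a single cut at 65. Age in years has no row in the schedule, but criterion 3.1.8 (Cockcroft-Gault) and the eGFR formula in Appendix I cannot be computed without it.
- **Severity.** Section 5.2 has two levels, ordinal score 3-4 and score 5. By the scale in 12.0, score 3 is no oxygen, score 4 is mask or prongs, and score 5 is high-flow oxygen or non-invasive ventilation.
- **Primary endpoint (13.4).** The first comparison is an unadjusted Z-test. A Cochran-Mantel-Haenszel test on age group and severity follows, then a logistic model "controlling for covariates of interest (gender, symptom onset, comorbidities) along with stratification factors".
- **Secondary endpoints (13.5).** For mortality: "Cox proportional hazards model will be used to compare treatment arms with inclusion of stratification factors or adjustment for covariates of interest". The proportional odds model has treatment arm and baseline severity only.
- **Sample size (13.6).** 132 per arm, 80% power, two-sided 0.05, with the treatment-arm proportion "80% under the null hypothesis and 92% under the alternative hypothesis". "The test statistic used is the two-sided Z-Test with unpooled variance".

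**The concern.** The primary outcome is death or respiratory failure at Day 28, and respiratory failure is defined largely by the level of oxygen or ventilatory support. Graded oxygenation at entry and age are therefore natural candidates for prognostic covariates. A cut at 65 treats patients of 30 and 64 as alike, and patients of 66 and 90 as alike. The lower severity level likewise treats a patient breathing room air and one on mask oxygen as the same. Few levels suit minimisation, but nothing obliges the analysis model to keep them.

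What is at stake is precision, not validity. Randomisation protects the comparison either way. But only about 37 failures are expected, and prognosis that the model leaves unexplained widens the interval of the adjusted estimate.

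**Working it through.** **1. The plan's own figure.** Inputs from 13.6: proportions 0.80 and 0.92, 132 per arm, two-sided 0.05.

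- SE (unpooled) = √[(0.80×0.20 + 0.92×0.08)/132] = √(0.2336/132) = 0.04207.
- Power = Φ(0.12/0.04207 − 1.96) = Φ(0.892) = 81.4%. With pooled variance it is 80.6%.
- n per arm for 80% power = (1.960 + 0.842)² × 0.2336/0.12² = 127.4, so 128 unpooled; 131 pooled.
- 95% half-width = 1.96 × 0.04207 = 8.2 points.

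The stated 132 and 80% are reproduced to within a few patients. No covariate enters the formula, so the choice of covariates cannot lower this figure.

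**2. Information available.** Expected failures = 132×0.20 + 132×0.08 = 26.4 + 10.6 = 37.0.

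**3. What finer covariates might add.** The documents give no prognostic strength for age or SpO2/FiO2 (S/F) and no severity mix, so these are assumptions. Two sets were simulated with 132 per arm, marginal rates fixed at 80% and 92%, and 3,000 trials per scenario. The adjusted estimate is a standardised risk difference from a logistic model. The strata column contains the age cut and the two-level severity. The Monte Carlo standard error of an entry near 85% is √(0.85×0.15/3000) = 0.65 points.

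*Set A:* age about N(62, 15); 40% severe, with log-odds of success −1.0; log-odds per 10 years of age −0.4, −0.6 or −0.8; log-odds per SD of S/F within severity 0.5, 0.8 or 1.2; critical value 1.97.

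| Assumed effects | Z-test | Strata | Age in years | Age in years + S/F | Gain over strata | Half-width, strata → full |
|---|---|---|---|---|---|---|
| Weak | 80.4% | 82.7% | 83.1% | 85.3% | +2.6 | 8.0 → 7.8 |
| Moderate | 82.1% | 85.0% | 85.4% | 87.9% | +2.9 | 8.0 → 7.5 |
| Strong | 81.8% | 84.9% | 86.5% | 91.5% | +6.6 | 7.9 → 7.1 |

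A second run of Set A gave gains of 1.4, 3.8 and 6.3 points (83.4 → 84.8, 83.3 → 87.1, 84.2 → 90.5). Half-widths went from 8.1 to 7.9, 8.0 to 7.6 and 7.9 to 7.2.

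*Set B:* age mean 60, SD 16; about 25% at score 5; latent correlation 0.7 between low S/F and score 5; correlation −0.2 between age and S/F; critical value 1.96. Half-width is 1.96 × the simulated SD.

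| Log-odds per SD age / per SD S/F / score 5 | Z-test | Strata | Age in years | Age in years + S/F | Gain over strata | Half-width, strata → full |
|---|---|---|---|---|---|---|
| 0 / 0 / 0 | 83.2% | 82.4% | 82.4% | 82.1% | −0.3 | 8.2 → 8.2 |
| 0.3 / 0.3 / 0.4 | 82.4% | 82.5% | 82.2% | 83.0% | +0.5 | 8.3 → 8.3 |
| 0.5 / 0.5 / 0.5 | 82.4% | 83.7% | 84.4% | 84.8% | +1.1 | 8.2 → 8.1 |
| 0.8 / 0.5 / 0.7 | 82.4% | 84.9% | 85.9% | 86.4% | +1.5 | 7.8 → 7.7 |
| 0.8 / 0.8 / 0.8 | 81.7% | 86.2% | 87.3% | 89.3% | +3.1 | 7.8 → 7.5 |
| 1.0 / 1.0 / 0.8 | 81.4% | 87.1% | 88.5% | 90.6% | +3.5 | 7.8 → 7.4 |

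**4. Where the gain comes from.** Replacing the cut by age in years adds 0.4, 0.4 and 1.6 points in Set A and −0.3 to +1.4 in Set B. S/F adds a further 2.2, 2.5 and 5.0 points in Set A and 2.0 and 2.1 in the two strongest Set B rows. Where S/F is assumed weaker in Set B, the two contributions are small and within simulation error of each other.

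**5. Type I error.** Null rejection across methods was 4.3% to 5.3% in Set A. For the fully adjusted risk difference it was 5.5% and 5.6% in Set B (Monte Carlo standard error about 0.4 points).

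**The case against.** The strongest reply is that nothing here is an error. Adjusting for the randomisation factors in the form in which they were stratified is a defensible choice, and the supportive models carry no power claim. That stands.

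Four stronger readings are tempting, and the documents do not support them:

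- *That the trial loses some of its 80% power.* It does not. That figure is for the unadjusted Z-test, which is also the first-named primary comparison. Changing the logistic model leaves that test as it is.
- *That oxygenation is ignored.* The severity stratum is a level of oxygen support, and it enters the Cochran-Mantel-Haenszel test, the logistic model, the proportional odds model and a subgroup. Only the finer measure is unused.
- *That the age cut is imposed on every secondary model.* The Cox model leaves its covariate list open, so age in years is not excluded, merely not prespecified. The proportional odds model has no age term at all.
- *That both values exist for every patient.* That is what the schedule intends; completeness is not established.

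The size is also open to challenge. The prognostic strengths are assumed, the largest gain needs a strong S/F effect within severity levels, and the gain disappears if the covariates are not prognostic. The simulated strata model omits gender, symptom onset and comorbidities, so any prognosis they share with age or S/F is credited to the change. Set B used simple allocation and no missing data. These points shrink the benefit but do not remove the reason to specify the covariates.

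**Conclusion.** The point holds as a missed opportunity, not a defect. Measurements that are already scheduled are left out of the adjusted analyses, and what replaces them is coarse.

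Relative to the planned strata, the expected benefit runs from about 0 to a little over 6 points of power (two runs of the most favourable case gave 6.6 and 6.3) and about 0 to 0.8 points of 95% half-width. Most of it comes from SpO2/FiO2 when that is strongly prognostic. All of this rests on assumed prognostic strengths and on linear effects.

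Relative to the unadjusted Z-test the range is wider: from 82.1 − 83.2 = −1.1 points with no prognostic effect to 91.5 − 81.8 = +9.7 in the strongest case. Part of that already comes from the planned strata, and it reaches the primary inference only if the adjusted risk difference is made the primary comparison.

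**What to change.** Keep 5.1 and 5.2 as minimisation factors. Then, in the analysis sections:

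1. In the 13.4 logistic model, replace the age cut by age in years (linear) and add baseline SpO2/FiO2 (last value before randomisation) beside the severity stratum. State a simple rule for a missing baseline value and how FiO2 is assigned for patients on mask or prongs.
2. From that model, report the standardised risk difference with a 95% interval next to the Z-test result, so that both are on the same scale.
3. In 13.5, name the same two covariates in the Cox model and add them to the proportional odds model.
4. State whether the Z-test or the adjusted risk difference is the primary comparison. If it is the latter, say so before outcomes by arm are seen, and say which statistic the interim boundaries apply to. The first look would have only about 33×0.20 + 33×0.08 = 9.2 failures, too few for a full model.

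The cost is wording and two data rules; no new measurement is needed. The model already has at least six terms (treatment, age, severity, gender, symptom onset, comorbidities), or 37/6 ≈ 6.2 failures per term. Adding SpO2/FiO2 makes that 37/7 ≈ 5.3. Age and SpO2/FiO2 should therefore take priority over weaker covariates, and age is better kept linear than splined.

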## 5.0 Stratification Factors

- 5.1 Age:  $\geq 65$  vs.  $< 65$  years
- 5.2 Clinical status ordinal score at enrollment: 3-4 (hospitalized with mild disease) vs. Score 5 (hospitalized with severe disease)

## 6.0 Registration/Randomization Procedures

### 6.1 Registration Procedures

6.1.1 To register a patient, access the Research Registration Application at [REDACTED] The Research Registration Application is available 24 hours a day, 7 days a week. Back up and/or system support contact information is available on the website. If unable to access the website, contact Research Registration Office at [REDACTED] between the hours of 8 a.m. and 4:30 p.m. Central Time (Monday through Friday).

Access and training instructions for the Research Registration Application are available on the Office of Clinical Trials web page [REDACTED]

#### 6.1.2 Verification of materials

Prior to accepting the registration, registration/randomization application will verify the following:

- IRB approval at the registering institution
- Patient eligibility
- Existence of a signed consent form
- Existence of a signed authorization for use and disclosure of protected health information

#### 6.1.3 Documentation of IRB approval

Documentation of IRB approval must be on file in the Registration Office before an investigator may register any patients.

In addition to submitting initial IRB approval documents, ongoing IRB approval documentation must be on file (no less than annually) at the Registration Office [REDACTED] If the necessary documentation is not submitted in advance of attempting patient registration, the registration will not be accepted and the patient may not be enrolled in the protocol until the situation is resolved.

When the study has been permanently closed to patient enrollment, submission of annual IRB approvals to the Registration Office is no longer necessary.

#### 6.1.4 Correlative Research

#### 6.1.4.1 Mandatory

A mandatory correlative research component and banking is part of this study, the patient will be automatically registered onto this component (see Sections 3.0, and 9.0).

#### 6.1.5 Banking

At the time of registration, the following will be recorded:

- Patient has/has not given permission to store and use his/her sample(s) for future research of SARS-CoV-2 infection.
- Patient has/has not given permission to store and use his/her sample(s) for future research to learn, prevent, or treat other health problems.
- Patient has/has not given permission for MCCC to give his/her sample(s) to researchers at other institutions.

#### 6.1.6 Pretreatment

Pretreatment tests/procedures (see Section 4.0) must be completed within the guidelines specified on the test schedule.

#### 6.1.7 Treatment

Treatment cannot begin prior to registration and must begin  $\leq$  5 days after registration.

#### 6.1.8 Kits are available on site.

### 6.2 Randomization Procedures

6.2.1 The factors defined in Section 5.0, together with the registering membership (site of institution) will be used as stratification factors.

6.2.2 After the patient has been registered into the study, the values of the stratification factors will be recorded, and the patient will be assigned to one of the following treatment groups using the Pocock and Simon dynamic allocation procedure which balances the marginal distributions of the stratification factors between the treatment groups.

All patients must be registered before starting therapy. Under no circumstances will non-registered patients be retrospectively eligible for the study.

### 6.3 Procedures for Double-Blinding the Treatment Assignment

6.3.1 After the treatment assignment has been ascertained by the registration/randomization application, the patient's treatment assignment (SOC treatment + Camostat mesilate OR SOC treatment + placebo) will be electronically sent to McKesson's Clinical Research Services. Upon receipt of orders, McKesson will send per patient supplies to participating institutions. The Camostat mesilate/placebo will be prepared and labeled by McKesson.

## 7.0 Protocol Treatment

7.1 Patients will be randomized to either the control arm (placebo) or the treatment arm (camostat).

**Control Therapy Placebo combined with SOC:** Patients will be randomized 1:1 to camostat or placebo taken as 2 tablets four times daily on an empty stomach at least 30 minutes before each meal, 2 hours since the last meal, and at bedtime. Remdesivir will be administered once daily IV for 5 or 10 days. Remdesivir must be obtained commercially. Remdesivir will not be supplied for this study. Other management decisions are left to the discretion of the treating physicians and may include any medicines deemed necessary and appropriate such as anticoagulation.

Agent	Dose Level	Route	Day
Camostat or placebo	200 mg four times daily on an empty stomach 30 minutes before each meal, 2 hours since last meal, and at bedtime	PO/NG €	1-14
Remdesivir¥	200 mg	IV	1
Remdesivir¥	100 mg	IV	2, 3, 4, 5 (5 day course) OR 2, 3, 4, 5, 6, 7, 8, 9, 10 (10 day course per local provider recommendation§)
Anticoagulation	Per institutional standard		

¥ The suggested dose is for adults and pediatric patients weighing  $\geq 40$  kg.

§ A treatment course of 10 days is recommended for adults and pediatric patients requiring invasive mechanical ventilation and/or extracorporeal membrane oxygenation. A treatment course of 5 days is recommended for adults and pediatric patients not requiring invasive mechanical ventilation and/or ECMO. If a patient does not demonstrate clinical improvement, treatment may be extended for up to 5 additional days (i.e. a total of 10 days).

€ Doses may be administered via NG tube by dissolving tablets in 55 ml of warm water until tablets dissolve into solution. Resulting solution can be administered via NG tube. Note, if a patient is on continuous tube feedings, camostat doses must be held.

## 7.2 Dose Modifications

Treatment discontinuation in the event of investigator assessed treatment associated toxicity rather than dose reduction.

Missed doses should not be replaced. Rather, treatment should resume with the next scheduled dose. Doses missed due to clinical inability to administer the dose (e.g. patient is undergoing a procedure at the scheduled time) shall not be counted as a protocol deviation and should simply be recorded as “unable to give dose”.

## 7.3 Breaking Codes in Double-Blinded Studies

7.3.1 In the event of an emergency, email the Research Registration Office at [REDACTED] to break the code on Monday through Friday, 8:00 a.m. to 4:30 p.m. Central Time. If the code must be broken after hours, assume the patient was assigned to active treatment and treat accordingly. Send an email to the Research Registration Office informing them of the need to un-blind a patient. Provide your contact information so that the personnel can respond to the email the next business day.

7.3.2 If, in the judgment of the attending physician, it would be helpful for the future clinical care of the individual patient, the code may be broken *after* the patient has completed the study. That is, after the patient has been fully evaluated and all evaluation information has been recorded by the attending physician and the patient (if appropriate), the Research Registration Office may be emailed at [REDACTED] to find out which study therapy the patient was receiving.

